5.5.2 Intervention Administration

Patients assigned to the brief behavioral intervention for dyspnea will participate in two sessions. The first session will occur at the patients' next scheduled clinic visit (either in the infusion suite or the outpatient clinic) via telephone, or via secure video following baseline data collection. The first session must occur within six weeks of the baseline data collection. Chemotherapy regimens for patients with advanced lung cancer are typically administered every two to three weeks. Thus, the six-week window will allow all enrolled patients to have a scheduled appointment, with additional time should their treatment be delayed for any reason (e.g., holidays or low blood counts). In the unlikely event that the patient is unable to come to the hospital for the first intervention session before the six-week window closes, the patient will be mailed the necessary study materials and receive the first session over the telephone or via secure video to remain in window. In the rare cases that the patient is still unable to complete the first session before the six-week window closes, the patient will be re-administered their baseline assessments either at their next appointment or by mail, telephone, or online via REDCap. Study procedures will reset from the new baseline assessment.

The second session will occur at the patient's subsequent clinic visit, over the telephone, or via secure video, within eight weeks of the baseline data collection.

Participants in both arms of the study will receive usual care for their dyspnea under the care of their clinicians.

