Once the oncology health care team has been informed and has not refused study staff to approach their patient, a study staff member will approach the patient in the infusion unit outpatient clinic, or via telephone to inquire about their experience with dyspnea. If the patient reports having dyspnea, the trained study staff member will explain the study. If the patient indicates interest in the study, they will be asked to complete a brief single-item screen to determine if they meet eligibility criteria (i.e., shortness of breath ≥ 2 on MMRCDS) for participation. To decrease participant burden, this brief screening measure will be given prior to consent. For patients who are approached via telephone, the MMRCDS will be administered verbally, via mail, or electronically. If the patient screens ineligible, the patient will not be consented and their MMRCDS will be appropriately discarded by the study staff using HIPAA-compliant procedures immediately. Patients who report shortness of breath score of ≥ 2 on the MMRCDS breathlessness measure will be eligible to continue to the next stage of the study.

For patients who screen eligible on the MMRCDS, the trained study staff member will perform consent procedures and administer the baseline assessments. Following the completion of the baseline assessments, the patient will be randomized to receive the intervention or standard care.

Otherwise, given that patients with advanced lung cancer develop new symptoms over time, patients with a score of <2 on the MMRCDS who agree to be approached again will continue to be screened with the brief measure every three months.

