4.2.3 Baseline Completion

Patients will be asked to complete the baseline questionnaires in person, via mail, telephone, or electronically. Once patients complete baseline questionnaires, the study staff will provide them with a wrist actigraph and activity log. Patients will be instructed on the

proper use of the actigraph and told to wear it and complete the activity log for the following 3 days. When this 3-day period ends, a study staff member will call the participant and notify them of their study group assignment. Patients will either return the actigraph at their next clinic visit or will mail it back to study staff via FedEx paid for by the study.

Using data from our electronic billing systems, we estimate that approximately 480 patients with advanced lung cancer receive treatment at the MGH Cancer Center and DFCI per year. Although studies show that approximately 50% of patients with metastatic cancer endorse some degree of shortness of breath, we conservatively anticipate 30%-40% of patients will report shortness of breath ≥ 2 using the MMRCDS (resulting in approximately 140-190 eligible patients per year). Based on the high accrual rates observed in our previous supportive care studies, and low patient burden for the proposed trial, we estimate 60% accrual to this study. Thus, we will be able to achieve successfully our recruitment goal of 220 patients during the 4-year enrollment period.

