Session One (if randomized to dyspnea intervention group)	Within 6 weeks of enrollment and baseline data collection	
 Nurse interventionist delivers Session One either in clinic or virtually by phone or secure video Study staff will contact participant to schedule Session Two
Session Two (if randomized to dyspnea intervention group)	After session 1, within 8 weeks of enrollment	
 Nurse interventionist delivers Session Two either in clinic or virtually by phone or secure video
Follow-up – Week 8 Assessment	8 weeks after baseline data collection	
 Participant completes follow-up questionnaires either in person while in clinic or remotely via mail, REDCap email, or telephone. Study staff instructs participant to wear actigraph and log activity for the 3 days following the completion of their week 8 self-report assessments. Study staff collects actigraph and activity log from participant via mail. For the procedures listed above, the study staff member delivering the assessment will remind the patient not to inform them of whether they received the intervention for breathlessness.
Follow-up – Week 16 and 24 Assessments	16 and 24 weeks after baseline data collection	
 Participant completes follow-up questionnaires either in person while in clinic or remotely via mail, REDCap email, or telephone. For the procedures listed above, the study staff member delivering the assessment will remind the patient not to inform them of whether they received the intervention for breathlessness.

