5.5.1 Instrument Administration

A study staff member blind to group assignment will administer study assessments at baseline and multiple follow-up time points (at weeks 8, 16, and 24) with a +/- 2 week window to accommodate patient schedules. The assessment battery takes approximately 30 minutes to complete. The baseline and follow up assessments (at 8, 16, and 24 weeks) will occur either in clinic, by mail, telephone or online via REDCap. We selected the six-month time frame for follow-up assessment to evaluate the long-term impact of the intervention on patient outcomes while recognizing the limited life expectancy of patients with advanced lung cancer. The self-report measures have strong psychometric properties and been well validated in previous studies.

If a participant expresses that he or she is not willing or able to complete the self-report packet in full, the study staff will offer an abbreviated version containing the primary outcome assessments (MMRCDS, CDS, HADS, and FACT-L). This short form will only be offered if a patient initially refuses to complete the entire questionnaire packet. Each participant will receive the actigraph at enrollment and will be instructed to wear the watch for the 3 days following their baseline assessment. In preparation for Week 8 follow-up, participants will receive the wrist actigraph either in person in clinic or by mail.

Patients will be instructed to wear the actigraph device for the 3 days following the completion of their 8-week self-report assessment. After this 3-day period, study staff will arrange a FedEx pick-up to retrieve the actigraph device.

If a patient passes away while in possession of an actigraph, we will call the person identified as a contact in the Participant Locator Form to offer our condolences. We will also explain that we will send a prepaid envelope to them addressed to our study staff, and instruct them to place the actigraph in the envelope, seal it, and send the envelope back to us in the mail (USPS). If we cannot reach the patient's contact by phone, we will send the prepaid envelope along with a note offering our condolences and instructions on how to return the actigraph.

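### A missed Session One restarts the baseline and follow-up clock after randomization, in the intervention arm only, and the analysis plan does not say which baseline or time origin applies

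*Combined protocol and SAP*

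**What the plan says.** Section 4.1 sets the order of events: "Following the completion of the baseline assessments, the patient will be randomized to receive the intervention or standard care". Section 4.2.3 adds that the patient learns the arm shortly afterwards: "When this 3-day period ends, a study staff member will call the participant and notify them of their study group assignment".

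The contact table in Section 5.5 gives a first session to one arm only: "Session One (if randomized to dyspnea intervention group". Section 5.5.2 allows six weeks from baseline for it. A patient who cannot attend is mailed the materials and is to "receive the first session over the telephone or via secure video to remain in window". The last resort begins "In the rare cases that the patient is still unable to complete the first session before the six-week window closes": the baseline battery is given again, and "Study procedures will reset from the new baseline assessment". No limit on repeat resets is stated.

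Follow-up is timed from baseline. The Section 5.5 table places the later visits "16 and 24 weeks after baseline data collection" and treats week 8 the same way. Section 5.5.1 describes "multiple follow-up time points (at weeks 8, 16, and 24) with a +/- 2 week window to accommodate patient schedules".

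Sections 6.1.1 and 6.3.1 compare the arms at week 8 with adjustment for baseline. Section 6.4 starts from completers and then adds an intention-to-treat analysis. None of these sections mentions a repeated baseline or defines time zero.

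**The concern.** A baseline covariate protects a randomized comparison because it is measured before allocation. A re-administered baseline is measured after allocation, by a patient who knows the arm, and only in one arm. The outcome is then taken at a different distance from randomization. A usual-care patient whose care is delayed for the same reasons keeps the original baseline and the original clock, so the departure has nothing in the other arm to offset it.

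Three things follow. The week-8 contrast no longer compares like times for reset patients. The intention-to-treat analysis in Section 6.4 keeps these patients but leaves their baseline and time origin open, so that choice could be made after the data are seen, for the primary outcome. And a second baseline that only intervention patients can have may reveal the arm to the assessor whom Section 5.5.1 describes as blind.

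**Working it through.** **The plan's own figure.** Section 6.2 states 80% power for 200 completers, a difference of 0.40 SD and two-sided alpha 0.05. With 100 per arm, the normal approximation gives 0.807 and the t test 0.804. The figure reproduces and is not in dispute.

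**Timing.** A reset cannot occur until the six-week window has closed, so these are minimum times from the original baseline:

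| Nominal visit | Reset patient | Earliest, with −2 weeks | All other patients (±2 weeks) |
|---|---|---|---|
| Week 8 | more than 6 + 8 = 14 | more than 12 | 6–10 |
| Week 16 | more than 6 + 16 = 22 | more than 20 | 14–18 |
| Week 24 | more than 6 + 24 = 30 | more than 28 | 22–26 |

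The windows do not overlap at any visit.

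**Size of the bias: assumptions.** The documents give no reset share, correlation, drift, selection or loss, so all are assumed:

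- a unit-variance score with correlation 0.5^(weeks/8) and no true treatment effect;
- worsening of 0 or 0.3 SD per 8 weeks;
- re-baseline at week 7 and outcome at week 15 for reset patients;
- reset either unrelated to dyspnea or correlated 0.3 with the week-7 score;
- loss among reset patients of none, the worst 30% on the week-7 score, or the worst 30% on the week-15 score.

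The analysis is ANCOVA using the new baseline and the late outcome. Negative values favor the intervention.

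**Two components by hand, at 5% resets.**

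- *Drift.* Seven extra weeks raise the outcome by 7 × 0.3/8 = 0.2625 SD. The new baseline rises equally, and a covariate slope of 0.5 removes half. Bias = 0.05 × 0.5 × 0.2625 = +0.007 SD. If the original covariate were restored but the late clock kept, it would be 0.05 × 0.2625 = +0.013 SD.
- *Selection.* If reset is correlated 0.3 with the week-7 score, the reset 5% average 0.3 × 2.063 = 0.619 SD at week 7 (2.063 is the mean of the top 5% of a standard normal). On the original clock they would contribute 0.619 × (0.5^(1/8) − 0.5 × 0.5^(7/8)) = 0.619 × 0.644 = 0.399 SD of baseline-adjusted excess. After the reset they contribute 0.619 × (0.5 − 0.5) = 0. Bias = −0.05 × 0.399 = −0.020 SD.

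**Simulation over all 12 combinations** (1.5 million per arm, chance difference removed):

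| Reset share | Bias range, SD | Without loss on the late outcome |
|---|---|---|
| 2% | −0.015 to +0.003 | – |
| 5% | −0.034 to +0.006 | −0.020 to +0.006 |
| 10% | −0.063 to +0.013 | −0.036 to +0.013 |

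**Variants.**

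- Original covariate with the late clock, 5% resets: −0.031 to +0.013 SD. Correcting the covariate alone is not enough.
- Original covariate and original clock: 0 if week 8 is collected; up to −0.017 SD at 5% if the same patients are still lost.
- Half of the resets occurring twice: −0.034 to +0.010 SD at 5% and −0.062 to +0.019 SD at 10%, so repeat resets add little.
- Rank-sum test on a five-level score with entry at 2 or more (35% at that level, the midpoint of Section 4.2.3's 30%–40%; other cutpoints assumed): −0.044 to +0.001 SD-equivalent at 5% and −0.086 to +0.002 at 10%.

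**Type I error**, 100 per arm: Φ(−1.96 + b/SE) + Φ(−1.96 − b/SE), with SE = √(2/100) = 0.141 unadjusted or √(2 × 0.75/100) = 0.122 adjusted. At the worst corners, b = 0.034 gives 5.7%–5.9% and b = 0.063 gives 7.3%–8.1%.

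**The case against.** The best defense has four parts.

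*Section 5.5.2 already answers the question.* Read with the visit table, it fixes the visit clock for a reset patient, and the new baseline is the natural covariate. That is fair for data collection. But the analysis sections do not adopt it, and if they did, the primary model would adjust for a post-randomization value in one arm. The natural reading is the problem, not the cure.

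*The reset is a third-line fallback.* It follows a six-week window and an offer of remote delivery, and the protocol expects few cases. This stands. The 5% and 10% shares have no support in the documents. At 2%, the worst bias of 0.015 SD moves the type I error only from 5.0% to 5.1%–5.2%.

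*The lower ends are built from assumptions.* This also largely stands. With reset unrelated to dyspnea and no loss, the bias at 5% is between 0 and about +0.007 SD. With selection, drift and no loss it is about −0.020 + 0.007 = −0.013 SD. The −0.034 corner needs selection, no drift and loss that depends on the late score, and that loss is partly a missing-data matter for Section 6.4. The sign cannot be settled in advance.

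*The remedy dilutes the effect and burdens ill patients.* The dilution is real and is costed under the fix. The burden is partly avoidable: a re-baseline taken promptly after week 6 falls inside the weeks 6–10 window and contains the primary measures, so it can serve as the week-8 assessment. This is not guaranteed, because the re-baseline may wait for the next appointment, and it does not cover weeks 16 and 24.

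**Conclusion.** The concern holds. The reset comes after randomization, can occur only in the intervention arm, and moves the nominal week 8 outside the window that applies to everyone else. The analysis plan names neither the baseline nor the time origin. It undercuts the intention-to-treat analysis in Section 6.4 without contradicting its wording.

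The expected effect is small: within about 0.015 SD of zero at 2% resets and 0.034 SD at 5%, against a 0.40 SD target, with uncertain sign. These figures illustrate the mechanism and are not bounds, since every input is assumed. The sample size is unaffected. The change should be made because a one-arm, post-randomization rule can be removed at little cost, not because a large bias is expected.

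**What to change.** State in Section 6 that, for every randomized patient, all efficacy analyses use the pre-randomization baseline and count weeks 8, 16 and 24 from it. Amend Section 5.5.2 so that outcomes are collected on that schedule even when Session One is late, and say whether a repeat battery falling within weeks 6–10 counts as the week-8 assessment. Use any repeat baseline only descriptively or in a sensitivity analysis. Report the numbers of resets and repeat resets. No change to session timing is proposed.

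The cost is SAP wording plus a short amendment, and possibly an extra 30-minute battery for a few patients. Some late starters will give a week-8 outcome before treatment. If all of them were untreated then, which is an upper bound, the effect falls to 0.98 × 0.40 = 0.392 SD (power 79%) at 2% late starters, or 0.95 × 0.40 = 0.38 SD (power 76%) at 5%. That loss is similar in size to the bias removed, but its direction is known and it does not raise the type I error. If the same patients are still lost at week 8, the bias of up to −0.017 SD at 5% remains as an ordinary missing-data problem.

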5.5.3 Special Concerns

Breach of confidentiality is a concern in all studies with human subjects. Patient participants will be completing self-report assessments; thus safeguards will be put in place to ensure that participant information is kept private and confidential. All electronic data will be stored in password-protected computer files and online databases (i.e. REDCap), accessible only to trained study staff. Participants' data will be identified by an ID number only, and a link between names and ID numbers will be kept in a separate password-protected computer file. Data will not be shared with individuals other than study staff.

5.5.4 Compensation

Study participants will not receive compensation for participating in this study or for completing questionnaires.

5.6 Adverse Reactions and Their Management

5.6.1 Reporting Adverse or Unanticipated Events

Identification of adverse events may come through notification from the study participant, caregiver, clinician, or from review of the electronic health record. In such circumstances, the PIs and investigative team will follow the following procedures:

- a. Serious Adverse Events. Given that this study is a randomized trial comparing a brief behavioral intervention compared to a usual care control group, we do not anticipate any study-related events meeting the FDA definition of a SAE (i.e., any fatal event, immediately life-threatening event, permanently or substantially disabling event, event requiring or prolonging inpatient hospitalization, or any congenital anomaly). The proposed study population is comprised of individuals diagnosed with advanced lung cancer who frequently experience disease worsening, high rate of symptoms, and hospitalizations from the underlying disease and/or side effects of treatment. Therefore, as advanced lung cancer is a chronic-type terminal illness, regular fluctuations in cancer-related symptoms, disease worsening, hospitalizations, emergency department visits, and deaths are to be expected throughout the study, and we will not consider or report such events as SAEs in this trial.
- b. Non-Serious Adverse Events. The IRB will be provided with unblinded summaries of study related non-serious adverse events by treatment group at the continuing reviews. These reports will include types of events, severity, and treatment phase. To date, the majority of non-serious adverse events in our prior supportive care studies have been due to patient discomfort with the study questionnaires.

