5.6.2 Anticipated Reactions

As this is a behavioral study, there are no ingested medications, and no biomedical procedures. It is unlikely that participants will be at any risk for physical harm as a result of study participation.

Participants may find some of the questions asked in the questionnaire to be emotionally upsetting, and may experience some fatigue from the length of the assessment battery. As this is a study targeting symptoms that are debilitating and interfere with quality of life, it is possible that some participants will experience depression and one of the major symptoms of depression, suicidality.

Participants may also find some of the breathing exercises from the dyspnea intervention uncomfortable during sessions and during home practice.

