The need for further intervention and referral regarding anxiety and depression symptoms will be determined by clinical cutoffs on the subscales of the Hospital Anxiety & Depression Scale (HADS) and by clinical assessment of the trained study nurse should any participant note heightened emotional distress and/or suicidality. Both the anxiety and depression subscales scores of the HADS range from 0 to 21, with a score of 11 or greater indicating definitive anxiety or depression. A score of less than 7 is considered normal, and a score of 8-10 on each subscale suggests probable anxiety and depression. Study patients whose scores increase from the normal or probably range to the more severe range for depression (i.e., ≥ 11) will be called by qualified study staff (e.g., [name], a licensed clinical psychologist, or similarly trained designee) to determine if the patient requires further intervention for his or her mood symptoms. Study staff will also assess for any suicidal ideation and ensure that the patient is not at any risk for self-harm. If the patient needs further outpatient services for depression, including pharmacotherapy, or is at risk for self-harm requiring hospitalization, study staff will make the necessary referrals for treatment. For example, for patients who are distressed but in no danger to self or others, study staff will refer either to the MGH Oncology Social Work Service or to the MGH Ambulatory Psychiatric Services [contact]), including the Cognitive-Behavioral Therapy Program. If suicidality or risk of harm to others is otherwise discovered at any study visit, the participant will be referred to appropriate services. Specifically, in the case that hospitalization is required, study staff will contact and escort the patient to the MGH Acute Psychiatry Service [contact]), with the aid of the MGH Police & Security if necessary [contact]). Study staff assessments of patient distress and/or risk will be documented in the electronic medical record so that the clinical team is notified of any potential need for increased support.

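### Section 5.6.1 gives a study-related serious adverse event no stated SAE or IRB report: admissions and deaths are excluded without a relatedness exception, and the IRB summary covers only non-serious events

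*Combined protocol and SAP*

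**What the plan says.** Section 5.6.1 of the combined protocol and SAP sets out how adverse events are handled once the team learns of them from a participant, caregiver, clinician or the health record.

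- Item (a), serious events, takes the FDA definition. It lists five criteria, among them any fatal event and any "event requiring or prolonging inpatient hospitalization". It gives an expectation: "we do not anticipate any study-related events meeting the FDA definition of a SAE". It then describes the population as one with frequent "hospitalizations from the underlying disease and/or side effects of treatment", and concludes that "hospitalizations, emergency department visits, and deaths are to be expected throughout the study, and we will not consider or report such events as SAEs".
- Item (b), non-serious events, contains the only report to an oversight body: "The IRB will be provided with unblinded summaries of study related non-serious adverse events by treatment group at the continuing reviews".
- Section 5.6.2, on anticipated reactions, says that "it is possible that some participants will experience depression and one of the major symptoms of depression, suicidality", and adds that the breathing exercises may be uncomfortable in sessions or at home.
- Section 5.6.3 covers a participant who "is at risk for self-harm requiring hospitalization, study staff will make the necessary referrals for treatment". The steps given are referral, escort to psychiatric services where admission is needed, and a note in the medical record. No safety report is mentioned.

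**The concern.** The exclusion is worded by type of event. The sentence before it speaks of admissions due to the disease or its treatment, but the list of events that will not be reported carries no cause against admissions, ED visits or deaths. Nothing says what happens if one of these is caused by a study session, home practice or an assessment, and nobody is asked to decide.

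At stake is oversight of the rare event that matters most. As written, mild discomfort from a breathing exercise reaches the IRB by treatment group, while an admission judged related to the study has no described path there. Section 5.6.3 already makes arrangements for one kind of admission, for self-harm risk, so the case is not far-fetched, even though the protocol does not call it study-related.

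**Working it through.** No calculation applies, since the point depends on no rate, effect size or sample size. The check is to set the rules side by side and follow particular events through them.

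**Step 1: what the exclusion removes.** Item (a) lists five seriousness criteria: death, immediate threat to life, lasting or major disability, admission (new or prolonged), and congenital anomaly. The exclusion names two of the five, death and admission. It also names ED visits, but an ED visit is not itself a listed criterion. A related ED visit that meets none of the five could still enter the non-serious summary in (b), so the gap concerns admissions and deaths.

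**Step 2: two readings of the exclusion.** Literal: every admission and death is excluded. Narrow: only those arising from the cancer or its treatment are excluded, because the sentence opens by appealing to the nature of advanced lung cancer and follows from the one before it.

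**Step 3: follow each event.**

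| Event | Literal reading of (a) | Narrow reading of (a) | In the IRB summary under (b)? |
|---|---|---|---|
| Related mild discomfort | Not serious | Not serious | Yes, by arm |
| Related admission | Not an SAE | An SAE, but no report described | No, it is serious |
| Related death | Not an SAE | An SAE, but no report described | No, it is serious |
| Related threat to life, no admission or death | An SAE, but no report described | The same | No, it is serious |
| Admission for cancer progression | Not an SAE | Not an SAE | No, as intended |

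In the three related serious rows, neither reading leads to a stated IRB report. The narrow reading changes the classification but supplies no assessor, recipient or time limit.

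**Step 4: where else the event would appear.**
- Medical record: section 5.6.3 requires staff assessments of distress or risk to be entered there for the clinical team.
- Team review: under section 5.6.3 the investigators and nurse interventionists meet at least monthly and go over adverse reactions.
- Outcome data: section 5.4.2 takes counts of ED visits and admissions from the health record after the study, and section 6.3.4 commits at least to describing their rates by arm.

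None of these is a report to an oversight body, and none is said to record relatedness. The section 5.4.2 list does not name deaths, so for a related death the team review is the only one of the three that the text clearly offers.

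**The case against.** The strongest reply is that the exclusion was never meant to cover study-caused events. Its sentence begins from the terminal course of lung cancer, follows directly from a statement about disease and treatment, and sits in a paragraph that opens with study-related events. That reading is natural, and it counts against the inference that the protocol plainly excludes every admission and death whatever its cause. The text is ambiguous rather than explicit. Even so, the narrow reading needs someone to decide cause, and it still states no report for an event that falls outside the exclusion.

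A second reply is that such events are captured elsewhere. This stands in part: a reader might infer that a related admission would leave no trace, and the record note, the monthly review and the by-arm counts show otherwise. What is missing is a stated SAE or IRB report.

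Third, a reader might infer that the protocol predicts serious self-harm caused by the study. It does not. Section 5.6.2 attributes possible suicidality to the symptoms being targeted, section 5.6.1 anticipates no study-related SAE, and no section mentions death by self-harm. The self-harm admission is an example only if it is judged related.

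Fourth, routine cancer admissions should not flood the IRB. That is right, and the exclusion should stay for them.

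Finally, the supplied text is incomplete. Section 4.2.2 refers to an appendix that is not shown, and institutional rules may add a route. The supplied text cites none for adverse events.

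**Conclusion.** The point holds in this form: section 5.6.1(a) lists admissions, ED visits and deaths as events not to be reported as SAEs, with no explicit exception for study-related events and no named assessor, while section 5.6.1(b) sends only non-serious related events to the IRB. On the supplied text, a study-related serious event has no stated SAE or IRB report under either reading.

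The reach is two of five seriousness criteria on the literal reading, for all 220 planned participants. The documents give no rate of related serious events, so the expected number cannot be stated; the protocol itself anticipates none.

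A reader might go further and infer that the trial's safety conclusion is undermined. The documents do not support that: sections 2.1 to 2.3 and 6.1.1 contain no safety aim, endpoint or hypothesis, and no bound on an SAE rate is planned. The defect is one of safety reporting. It should be corrected because the rule, followed literally, withholds the more serious related events while reporting the less serious ones. The conclusion assumes that no unseen appendix or institutional rule already supplies the route.

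**What to change.** Reword section 5.6.1(a) in three respects:

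1. Limit the exclusion to admissions, ED visits and deaths judged due to the cancer, its treatment or a comorbidity and unrelated to study procedures.
2. Name an existing investigator to make that judgement when the team learns of an event. The thoracic oncologist co-investigator who oversees health-record review in section 5.4.2 is a possible choice, but the outcome review described there is post-study and collects counts, so attribution at the time of the event would be a small added task.
3. State that any event that meets a listed seriousness criterion and is judged at least possibly related to a session, home practice or an assessment is reported to the IRB as an SAE. Extend the by-arm summary in section 5.6.1(b) to include these events.

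Self-harm events handled under section 5.6.3 should pass through the same two tests, seriousness and relatedness. Making all of them SAEs automatically would bypass the relatedness judgement that the rewording introduces. A cross-reference from section 5.6.3 to the revised rule would help.

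The cost is a one-paragraph amendment, a brief attribution entry per known event and possibly a few more IRB reports. The documents do not estimate how many admissions or deaths would need an entry. No intervention or assessment changes.
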